## Descriptive Variables

Baseline descriptive variables will be analyzed using standard methods as appropriate for the variable type (e.g. continuous, binary, ordinal, etc.) and empirical-derived distribution functions (e.g. parametric or non-parametric). To assess performance of proposed randomization stratification to inform future full-scale trials, baseline covariate balances between treatment arms will be compared using differences in empirical cumulative density functions (eCDF) and variance ratios.

## Subgroup Analyses

Exploratory subgroup analyses will analyze group differences in demographic factors like age, disease factors such as tumor grade, tumour location and deficit type (e.g. physical, cognitive, communication, etc.) on secondary outcome measures using linear mixed effects modeling for measures repeatedly administered following randomization. As these are exploratory in nature and under-powered to sufficiently detect group differences, effect estimates and their 95% CI will be reported and p-values will not be reported.

Thematic analysis will be used to analyze the collected data. The first five interview transcripts will be initially coded by two members of the research team, and they will then meet to compare their codes. This step will allow for enhanced reflexivity and ensure rigour. A coding framework will be developed and applied to the remaining transcripts.

To facilitate the organization and analysis of the qualitative data, the transcripts, will be entered into NVivo 11. Following this, the codes will be clustered into groups or categories (i.e., codes that share similar meanings) and the predominant themes will be identified.

To maximize credibility and trustworthiness, additional members of the research team will meet with the two members of the research team over several meetings to discuss the developing analysis. New themes will also be discussed. Together, they will explore various thematic maps until consensus is reached and theme labels are agreed upon. The two members of the research team will analyze the remaining data. To protect anonymity, quotes exemplifying the various themes will not include any identifying details on the participants.

## Trial Safety, Fidelity and Implementability Analyses

Recruitment rate, number and type of adverse events, number and reasons for dropouts, and numbers lost to follow-up will be summarized. At the end of the trial, semi-structured interviews will be completed with participants who have been randomized to receive telerehabilitation intervention to further explore the barriers and facilitators.

## **Participant Withdrawal**

#### Reasons for withdrawal

Participants may withdraw or be withdrawn from the trial for any of the following reasons:

- Participant withdraws further participation in trial for any reason
- Participant becomes unable to complete trial intervention and/or complete assessment visits)
- Any medical condition that, in the opinion of the PI, may jeopardize the participant's safety if they continue in the trial

## **Documenting participant withdrawal**

In all circumstances, reasons for withdrawal will be collected and all participants will be followed through to the trial's conclusion with previously stated outcome measures performed (timing is outlined in Table 1), as the main analysis will be an intention to treat analysis. This will, of course, be subject to the participant's continued consent to return for these assessments. Participants who withdraw consent will be advised to follow up with their regular health care provider.

Participants who are withdrawn or withdraw from active treatment will not be replaced.

#### **Discontinuation Criteria**

As stated above, an individual participant who suffers a Serious Adverse Event (SAE) judged to be related to the intervention will lead to discontinuation of the intervention. Principal investigators will be responsible for initiating appropriate medical care of participants at their site, and any rescue procedures will follow the best standard of care. Any events will be recorded. Unblinding of the participant allocation can be done if needed by the treating healthcare team.

For the trial as a whole, there are no planned interim analyses for efficacy or futility.

## Adverse Events and Serious Adverse Events Definition of an Adverse Event

An adverse event (AE) is an untoward medical occurrence in a participant that occurs during the course of the clinical trial which may or may not have a causal relationship with the trial procedures. An AE can be any unfavourable or

unintended sign (e.g., abnormal laboratory finding), symptom, or disease temporally associated with a trial procedure.

### **Definition of a Serious Adverse Event**

A SAE is defined as an AE that results in any of the following outcomes:

- Death
- Life-threatening situation (participant was in immediate risk of death at the time of the event. However, an event that might have hypothetically caused death if it was of greater severity is not included.)
- New in-patient hospitalization or prolongation of existing hospitalization
- Persistent or significant disability or incapacity
- Important medical events not resulting in death, be life-threatening, or requiring hospitalization but may jeopardize the participant and may require medical or surgical intervention to prevent one of the above outcomes (based upon appropriate medical judgment)

Handling of Serious Adverse Events Principal investigators will be responsible for initiating appropriate medical care of participants during the study, in connection with trial procedures and assessments, and for monitoring the safety of participants.

All SAEs will be assessed during the course of the trial. At the beginning of every assessment session participants will be asked if they have experienced any AEs. Therapists routinely ask patients about adverse events that occur as the result of therapy, and they will be asked to relay this information to the Principal Investigators. In case an SAE is reported, the delegated study clinician who examines and evaluates the participant will determine the event's causality to the trial's procedures, based on temporal relationship and his/h r clinical judgment. It is the responsibility of the Principal Investigators to ensure all SAEs are assessed to determine causality, that is, to determine the likelihood that the SAE was caused by a study intervention.

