## **Blinding**

Evaluators and the study statistician will be blinded to the group allocation, however, due to the nature of the intervention, participants and members of the research team cannot be blinded to group allocation.

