## **Secondary Outcomes**

- Recruitment Screening and recruitment efficiency, number of participants recruited, percentage of patients approached who consent to the trial
- 2. **Adherence to interventions** Percentage of rehab sessions attended, participant characteristics associated with adherence, percentage of participants who used BrainHQ/exercise programs and how much
- 3. **Retention** Follow-up rates, time needed for data collection
- 4. **Participant Experience** We will conduct semi-structured qualitative interviews with participants to better understand their telerehab experiences, the perceived impact of the intervention on quality of life, and barriers/facilitators for their participation in the intervention.

**Safety** - percentage of patients who experience adverse events, percentage of rehab sessions in which adverse events occurs, and adverse event type, severity and relatedness across both intervention groups.

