#### **Telerehab Intervention Protocol**

Participants randomized into the active intervention group will be asked to participate in an outpatient neuro-rehabilitation program via telerehabilitation starting **concurrently** with their radiation therapy. Currently, patients with gliomas with rehabilitation needs start rehabilitation after their radiation therapy. The neuro-rehabilitation program used in the study will be 8-weeks in duration, and identical to what we currently offer in the ABI day hospital with the exception of 1) the rehabilitation program start concurrently with radiation and 2) the

therapies will delivered via telerehabilitation for all participants (compared to the ABI day hospital currently delivers up to 1/3 of their therapy sessions via telerehabilitation.

The key components of the outpatient neuro-rehabilitation program in this study are:

- Participants will discuss with the ABI day hospital service coordinator their impairments and goals, to understand if they need physiotherapy, occupational therapy and/or speech language therapy based on their clinical needs
- They will have twice a week, 50min sessions for each type of therapy
- Therapy will be delivered via Microsoft Teams and/or phone, based on therapists' clinical judgment

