## Secondary Outcomes

Secondary outcomes (e.g. balance, mobility, quality of life, mood, etc.) are continuous in nature and will be analyzed using linear regression, adjusted for baseline. Time to all-cause mortality, time to disease specific mortality, and time to disease progression will be analyzed using Kaplan Meier estimators and logrank tests.

Disease and demographic factors that may influence protocol attrition and adherence will be analyzed using a generalized linear mixed effects model with an assumed unstructured covariance matrix structure and robust sandwich estimation.

To assess the safety of the protocol, the number, type, and severity of SA events will be reported as a cumulative incidence and compared between treatment arms using a Poisson regression.

Since these analyses are hypothesis generating, complete-case analyses will be used, p-values will not be listed and 95% confidence intervals of estimates and change scores will be used instead so the study results can be interpreted in context. The standard deviation of changes in secondary outcome measures will be used for sample size calculations for future full-scale studies.

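### Only the telerehab arm has a second route for reporting adverse events, the between-arm AE summary does not separate the routes, and the AE question is not kept from the blinded evaluators

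*Protocol*

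**What the plan says.** The paragraph on handling serious adverse events (Protocol, Definition of a Serious Adverse Event) sets up two routes by which AEs become known.

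- **Common to both arms:** "At the beginning of every assessment session participants will be asked if they have experienced any AEs".
- **Through therapists:** "Therapists routinely ask patients about adverse events that occur as the result of therapy", and therapists are to pass this on to the principal investigators.

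Under Intervention groups, usual care during radiation consists of exercise instructions and a BrainHQ subscription, with no therapist sessions. For the telerehab arm, the Telerehab Intervention Protocol section says "The neuro-rehabilitation program used in the study will be 8-weeks in duration" and "They will have twice a week, 50min sessions for each type of therapy". A service coordinator and the participant settle "if they need physiotherapy, occupational therapy and/or speech language therapy based on their clinical needs".

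The safety item under Secondary Outcomes (Outcome Measurements) covers the percentage of patients with AEs, the percentage of rehab sessions with an AE, and "adverse event type, severity and relatedness across both intervention groups". In the Statistical Analysis Plan section, SA events (read here as serious adverse events) "will be reported as a cumulative incidence and compared between treatment arms using a Poisson regression".

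On masking, the Blinding section says "Evaluators and the study statistician will be blinded to the group allocation". Participants and the rest of the research team are not blinded.

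**The concern.** There are two linked problems.

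**Unequal detection.** A strain, a near-fall or a dizzy spell is counted only if someone hears of it. In the telerehab arm a therapist may hear of it within days. In usual care a similar event during home exercise must be recalled at the next assessment, up to four weeks later in this period. If both sources feed one AE percentage, part of any excess in telerehab may come from closer questioning, and the data could not separate that part from real harm. Safety is named in the first study objective, so this summary will be read.

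**Masking.** The AE question comes at the start of a session in which blinded evaluators then administer tests such as the Berg Balance Scale and the Timed Up and Go. An answer that mentions a therapy session identifies the arm before scoring begins.

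**Working it through.** **Scheduled occasions.** The protocol gives no count of AE enquiries, so there is no stated figure to reproduce. The inputs are 2 sessions per week per discipline, 8 weeks, 1 to 3 disciplines (Telerehab Intervention Protocol), and assessments at weeks 4, 8, 12 and 26.

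- Common route, after baseline: 4 assessments in each arm, of which 2 (weeks 4 and 8) fall within the programme.
- Therapist route, telerehab only: sessions = 2 × 8 × number of disciplines.
  - One discipline: 2 × 8 × 1 = 16
  - Two: 2 × 8 × 2 = 32
  - Three: 2 × 8 × 3 = 48
- Therapist route, usual care during radiation: 0.

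The 16 to 48 are scheduled sessions, not AE enquiries. The protocol says therapists ask routinely, which need not mean every time, and their question concerns events caused by therapy.

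**Effect on the comparison.** Let both arms have the same true number of events per patient, and let d_T and d_U be the fractions that come to light in telerehab and usual care. The apparent ratio of event counts is then d_T / d_U, which equals 1 only if detection is equal. A second route can raise d_T but not d_U, so the ratio moves above 1, and the percentage of patients with at least one AE moves the same way. The protocol gives neither fraction, so no size can be derived. For deaths and hospital admissions both fractions should be near 1: if they were 1.00 and 0.98 (assumed, for illustration), the ratio would be 1.00 / 0.98 = 1.02.

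**Whether anything downstream corrects it.** The safety item does not distinguish the sources. The principal investigators classify severity and relatedness (Risks related to telerehab), but only for events already reported, and research team members are not blinded.

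**Masking, passages side by side.**

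- The AE question is put at the start of every assessment; who asks it is not stated.
- The 26-week section has evaluators checking at the start of evaluations whether caregivers may listen, so they are present at the opening.
- The 8-, 12- and 26-week sections have AEs noted as part of the evaluation.
- The 26-week list includes an interview for the telerehab arm only, with no statement of who conducts it.
- No section keeps the AE answers or the interview from the evaluator.

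**The case against.** Several objections have force.

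- **The general AE question is asked equally.** Both arms get it on the same schedule. A reader might add the sessions to the four assessments and infer that AEs of every kind are sought many times as often in telerehab. The protocol does not support that: the therapist question is limited to effects of therapy, its frequency is not given, and the ratio runs from about 4 to 25 depending on the counting rule. What stands is an extra route for a subset of events, and that subset enters the AE percentage and relatedness.
- **The only modelled safety comparison is of serious events.** A reader might infer that it too is biased. Serious events depend little on questioning, so this is not shown. Follow-up time and dispersion in that Poisson model belong in a statistical analysis plan that is not at hand, and the reference to cumulative incidence can be read as a separate reporting step.
- **Some separation is already planned.** The per-session percentage and the relatedness classification are both in the protocol. They help, but neither removes therapist-relayed events from the between-arm percentage.
- **Unblinding is not stated.** A reader might infer that evaluators will be unblinded. The protocol does not say that the evaluator asks the question, and the interview is listed last. What stands is the missing safeguard.
- **Nothing turns on a safety threshold.** A reader might infer that a spurious excess would decide whether a larger trial proceeds. The only stated criterion is at least 80% completing the 8-week protocol, and secondary analyses are declared hypothesis-generating.
- **Relying on scheduled recall could under-count harm.** This is fair, and it is why an all-sources table is needed beside the comparison.

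**Conclusion.** The point holds in a limited form. During the 8-week programme the telerehab arm alone has a second AE route, attached to 16 to 48 scheduled sessions if the full programme is delivered. The safety summary across arms does not separate it. The comparison of non-serious AEs is thus open to ascertainment bias against telerehab. The direction follows from the design; the size is unknown because the protocol gives no detection rates and no frequency of therapist questioning. Serious AEs are little affected.

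Separately, the AE question at the start of assessments is a plausible route to unblinding evaluators before they score performance tests. This is a gap in the plan, not a planned breach.

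The conclusion assumes that usual-care participants have no comparable therapist enquiry during radiation, as the Intervention groups section implies. Later day-hospital referral is open to both arms and is not part of the imbalance described here.

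**What to change.** 1. Base the between-arm AE comparison on one structured question, worded identically in both arms and asked at weeks 4, 8, 12 and 26, plus all serious AEs from any source.
2. Record the source of each AE in the eCRF. Report therapist-relayed events separately for the telerehab arm, using the per-session percentage already listed under Secondary Outcomes, and give an all-sources table alongside so that no harm is hidden.
3. Have an existing team member who is not an evaluator, such as the study coordinator, ask the AE question out of the evaluator's hearing.
4. Hold the telerehab-only week 26 interview after testing, with someone who is not an evaluator.

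The cost is protocol wording, one source field and some coordinator time at each assessment, with no added visits. The downside is that minor events known only through therapists leave the main AE contrast, though they are still reported. A residual imbalance may remain, since participants already questioned by a therapist may recall events better at the scheduled enquiry.

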## **Determining causality of Serious Adverse Events**

Degree of certainty about causality will be graded as follows:

- **Definitely Related:** Clear evidence to suggest a causal relationship and other possible contributing factors can be ruled out.
- **Probably Related:** Evidence to suggest a causal relationship and the influence of other factors is unlikely.
- Possibly Related: Some evidence to suggest a causal relationship but the influence of other factors may have contributed to the event.
- **Unlikely:** The temporal relationship to the trial procedures makes a causal relationship improbable and/or the SAE is more likely due to other factors such as concomitant medication(s) or concomitant disease(s).

• **Not related:** The SAE is completely independent of trial procedures, and/or evidence exists that the event is definitely related to another etiology.

## **Documenting Serious Adverse Events**

Pre-existing conditions will be recorded at the baseline visit following participant enrolment (including start date of the condition, frequency, and severity). After the participant signs the informed consent form any worsening of these conditions will be documented.

SAEs experienced by the participant between the signing of the Informed Consent and completion of the final follow-up appointment (the 26-week visit) will be recorded in the electronic case report form (eCRF).

## Following up on Adverse Events

The principal investigators will follow participants with AEs until the events have subsided, the conditions are considered medically stable, the investigator considers it medically justifiable to terminate follow-up, or the participants are no longer available for follow up. Participants who discontinue due to adverse events will be treated and followed according to established medical practice. All pertinent information will be entered into the eCRF.

All SAEs should be monitored until resolved or until the SAE is clearly determined to be due to a participant's stable or chronic condition or intercurrent illness(es).

## **Reporting Serious Adverse Events**

AEs experienced by the participant between the signing of the Informed Consent and completion of the final follow-up appointment (the 26-week visit) be reported to the principal investigator. The study team will report SAEs and Safety Reports to the UHN REB as per institutional requirements.

#### **Data Collection and Methodology**

All eligible participants will be consented prior to the initiation of any portion of the study assessments and intervention. The principal Investigator will review the baseline data and ensure that the participant meets the eligibility criteria and has provided informed consent.

Data will be managed in accordance with good clinical practices (GCP) for research trials involving human subjects.

The CRFs will be completed in a timely manner. All study records will be kept in accordance with applicable laws and regulations.

#### **Record Retention**

All trial records will be maintained and retained for a period of 10 years per current University Health Network Regulations.

## **Confidentiality and Participant Data Protection**

The participants will be informed that data will be stored and analyzed by computer. The data will be stripped of participant identifiers prior to storage and a study ID will be assigned to each participant upon enrollment into the study. The document linking the study ID to the participant's name will be kept separately from the other files in a secure location. All participant information will be kept confidential and the participant will not be recognizable in data submitted for publication.

Records for each participant in the study will be de-identified and maintained in separate files in a secure, limited access location at the study site.

## **Publications**

The results and experiences derived from this study will be jointly published by the investigators in the appropriate medical journals and presented at professional conferences.

